4.5.6.3 Interim Analyses and Data Monitoring

In addition to the Stage 1 analysis specified by Simon's decision criteria for proceeding to Stage 2, a formal interim analysis will be performed for a post-Stage 2 expanded lymphoma subtype cohort overall and for patients with second-line EBV⁺ lymphoma. A total of 40 second-line EBV⁺ lymphoma patients who have been followed for at least 6 months or permanently discontinued study treatment, will be used for the interim analysis. For these interim analyses, the observed ORR by IRC will be evaluated along with the 95% confidence interval. Other secondary endpoints will be evaluated with descriptive statistics such as both point and interval estimates.

The final efficacy analysis will be performed as planned with a total 120 patients with relapsed or refractory EBV⁺ lymphoma patients enrolled in the post-Stage 2 expansion phase of the study, which are anticipated to include approximately 50-60 patients with second-line EBV⁺ lymphoma. The final analysis will be performed when all patients, including those with second-line EBV⁺ lymphoma have been followed for at least 6 months or permanently discontinued study treatment. If at least 26 responses are observed for an ORR ≥65% (95% CI: 79%, 48%) at interim analysis of 40 patients with second-line EBV⁺ lymphoma, then overwhelming efficacy would be declared to potentially support accelerated NDA submission after these patients are followed for at least 6 months for DOR and other secondary endpoints. This magnitude of treatment effect at the interim analysis would exclude an approximately 47% ORR with 95% confidence. Of note, enrollment into any post-Stage 2 expansion cohort would continue to complete the planned enrollment of 120 patients for the final analysis independent of the interim analysis outcome.

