3.3.2 Method of Assigning Patients to Cohorts

Patients will be enrolled utilizing Simon's 2-stage design options for discontinuing enrollment into each cohort where treatment appears to be futile. In Stage 1, 6 cohorts (Cohorts 1, 2, 3b, 4, 5, and 6) will enroll up to 10 patients each. Patients will be enrolled into each cohort based on their primary lymphoma diagnosis to receive the combination nanatinostat plus valganciclovir with exception of Cohort 3a.

The first 20 patients enrolled with PTCL in Cohort 3 will be randomized 1:1 to either Cohort 3a (nanatinostat monotherapy) or Cohort 3b (nanatinostat plus valganciclovir). Randomization will occur at the time of drug dispensation for Cycle 1 Day 1. Following a disease response assessment at 6 weeks, patients in Cohort 3a with a CR or PR will continue nanatinostat monotherapy. Those in Cohort 3a with stable disease at 6 weeks or disease progression at any time will be offered the option to cross over to receive combination therapy for the remainder of the study, provided they qualify per hematology, chemistry, no sign of CNS disease progression, and ECOG performance status parameters.

All cohorts that have a response in 2 or more patients in Stage 1 will expand enrollment by 11 patients in Stage 2, for a total of 21 patients in each cohort (Figure 2). If \geq 7 responses are observed in the initial 21 patients in any cohort, then enrollment will be expanded to include up to 120 additional patients in that cohort (N=141), with an interim analysis of efficacy and safety planned in the second-line EBV⁺ lymphoma

subpopulation (see Section 4.7 for sample size details). Data from a total of 40 patients who have been followed for at least 6 months or permanently discontinued study treatment will be used for this interim analysis. If the interim efficacy analysis outcome is positive (see Section 4.5.6.3 for details of this interim efficacy analysis), then the final analysis would still be conducted for all second-line EBV⁺ lymphoma patients and the entire cohort. Cohort 3a will not enroll beyond the initial 10 patients, regardless of the number of responders in Stage 1. See Section 4.7 for details.

Cohort 7 will be closed to enrollment when all other cohorts are closed, or sooner at the discretion of the Sponsor, regardless of the number of patients recruited at that time and will not be subject to the decision criteria of the Simon's 2-stage design.

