A formal interim analysis will be performed for each post-Stage 2 expanded lymphoma subtype cohort in patients with second-line EBV⁺ lymphoma when a total of 40 second-line EBV⁺ lymphoma patients have been followed for at least 6 months or permanently discontinued study treatment. The rationale for selecting 40 patients at the interim analysis is provided in Table 4 below using the Clopper-Pearson binomial confidence intervals of the proportion (Clopper 1934).

Table 4 Sample Sizes for the Interim and Final Analyses of Patients with Second-Line EBV⁺ Lymphoma

Sample Size	Observed Rate	95% CI	Control Rate
	42.5%	(59%, 27%)	25%
40	52.5%	(68%, 36%)	35%
	65%	(79%, 48%)	45%
	40%	(55%, 26%)	25%
50	50%	(64%, 36%)	35%
	62%	(75%, 47%)	45%
	38%	(52%, 26%)	25%
60	48%	(61%, 35%)	35%

Sample Size	Observed Rate	95% CI	Control Rate
	60%	(72%, 46%)	45%

If the observed effect is 52.5% (i.e., 21 responders out of 40 patients) at the interim analysis, then the 95% CI will exclude an ORR effect size of 35%. For these interim analyses, the observed ORR by IRC will be evaluated along with 95% CI. Other secondary endpoints will be evaluated with descriptive statistics such as both point and interval estimates.

The final efficacy analysis will be performed as planned with total 120 patients in the expansion stage of the study. Approximately 50-60 patients with second-line EBV⁺ lymphoma are anticipated to be enrolled at the time of the final analyses. The final analyses will be performed when all patients, including second-line EBV⁺ lymphoma patients, have been followed for at least 6 months or permanently discontinued study treatment.

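### The SAP does not say which 40 second-line patients form the interim set; read as the first 40 to qualify, the rule biases the interim ORR downward

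*SAP*

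**What the plan says.** Three SAP sections describe the interim set, each by patient status:

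- SAP 4.5.6.3: 40 second-line patients "who have been followed for at least 6 months or permanently discontinued study treatment, will be used for the interim analysis".
- SAP 3.3.2: "Data from a total of 40 patients who have been followed for at least 6 months or permanently discontinued study treatment".
- SAP 4.7 times the interim to the moment when 40 second-line "patients have been followed for at least 6 months or permanently discontinued study treatment".

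None of them orders the patients by enrolment or first dose, and none gives a data cut-off rule.

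The set feeds a decision. SAP 4.5.6.3 states: "If at least 26 responses are observed for an ORR ≥65% (95% CI: 79%, 48%) at interim analysis of 40 patients". In that case overwhelming efficacy is declared, possibly in support of an accelerated submission, and the section adds: "This magnitude of treatment effect at the interim analysis would exclude an approximately 47% ORR with 95% confidence". Expansion enrolment continues to 120 whatever the interim shows, with about 50 to 60 second-line patients expected by the end.

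Three other provisions matter. Treatment runs until progression as judged by the investigator (SAP 3.1). Scans are every 8 weeks up to week 24. Non-evaluable patients count as non-responders and stay in the denominator (SAP 4.5.6.2).

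**The concern.** A patient meets the condition at the earlier of two times: 6 months of follow-up, or permanent discontinuation. A patient who progresses early meets it early. A responder still on treatment meets it only at 6 months.

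Since accrual continues, some second-line patients will normally have been enrolled within the 6 months before the cut. If the 40 are taken in order of qualifying, the failures among these recent patients are counted and most of the equally recent responders are not. Entry to the set then depends on outcome. The observed rate no longer estimates the ORR of second-line patients, and the exact binomial interval, which assumes an unselected 40, is centred too low.

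At stake are the interim ORR estimate and the chance of reaching 26/40 when the treatment works.

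**Working it through.** **Inputs from the documents.** n = 40, threshold 26, Clopper-Pearson 95% interval (SAP 4.5.6.3, 4.7); 50 to 60 second-line patients in all (60 used below); first scan at 8 weeks, which is 56/30.4375 = 1.84 months using the month length in SAP 4.1.5.

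**Assumptions, because the documents do not give these values.** Second-line accrual λ = 1, 2, 4 or 8 per month. Median time on treatment of non-responders: 2 months (about the first scan) or 3.7 months (the median PFS that Protocol 1.1.2 cites for chemotherapy at PTCL relapse). Responders: 1.84 months plus a median of 6.5 or 17.1 months (the DOR figures in Protocol 1.2.4 for all evaluable patients and for PTCL). Times are exponential.

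**Step 1: the plan's own figure.** 26/40 = 65.0%, with exact limits 48.3% and 79.4%. This matches the SAP and its statement about excluding roughly 47%. For an unselected 40, P(X ≥ 26) is 0.572 at a true ORR of 65% and 0.0086 at 45%.

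**Step 2: the expected interim ORR if the first 40 to qualify are used.** Let W be the mean wait from enrolment to qualifying, that is, the mean of min(6 months, time to discontinuation), for responders (R) and non-responders (N). While accrual continues, the expected numbers qualified by time t ≥ 6 are λp(t − W_R) responders and λ(1 − p)(t − W_N) non-responders. Setting the sum to 40 gives, approximately,

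bias in ORR = −λ p(1 − p)(W_R − W_N)/40.

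The mean waits are:

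- W_N, median 2: (2/ln 2)(1 − 2^(−6/2)) = 2.885 × 0.875 = 2.52 months.
- W_N, median 3.7: 5.338 × 0.675 = 3.60 months.
- W_R, median 6.5: 1.84 + (6.5/ln 2)(1 − 2^(−4.16/6.5)) = 1.84 + 3.36 = 5.20 months.
- W_R, median 17.1: 1.84 + 3.83 = 5.67 months.

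Example with p = 0.65, λ = 2 and medians 2 and 6.5: 2 × 0.2275 × (5.20 − 2.52)/40 = 0.030, so the expected interim ORR is 62.0%.

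**Step 3: simulation.** Poisson enrolment, 20,000 runs per setting, true ORR 65%. Each cell gives expected interim ORR, then P(≥ 26/40). The first 40 enrolled give 65.0% and 0.57 throughout.

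| Medians, N / R (months) | 1/month | 2/month | 4/month | 8/month |
|---|---|---|---|---|
| 2 / 6.5 | 63.5%, 0.50 | 61.9%, 0.41 | 58.9%, 0.27 | 55.4%, 0.15 |
| 2 / 17.1 | 63.3%, 0.49 | 61.4%, 0.39 | 57.9%, 0.23 | 54.1%, 0.12 |
| 3.7 / 6.5 | 64.2%, 0.53 | 63.2%, 0.47 | 61.4%, 0.38 | 59.7%, 0.31 |
| 3.7 / 17.1 | 63.8%, 0.51 | 62.6%, 0.45 | 60.4%, 0.33 | 58.1%, 0.24 |

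The formula agrees with the simulation to about 0.1 point up to 4 per month. At 8 per month all 60 patients are usually enrolled before the cut, and the formula overstates the bias. A milder setting (medians 3.7 and 8.5 months, with no minimum time for responders) gives a bias of about 0.7 point and P = 0.54 at 1 per month. With 50 second-line patients instead of 60 and medians 2 and 17.1, the result at 2 per month is 61.5% and 0.39.

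**Step 4: direction.** At a true ORR of 45%, P(≥ 26/40) falls from 0.009 to 0.007 or less in every setting.

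**Step 5: when the effect disappears.** If responders leave about as fast as non-responders (medians 1.5 months after the first scan and 3.7 months), the expected ORR is 64.9% at 2 per month and 64.7% at 4 per month.

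**The case against.** The strongest reply is that the SAP never says the 40 are the first to qualify. The same phrase governs the final analysis in 4.5.6.3 and 4.7, where it is plainly a maturity condition on all patients. Read that way at the interim, with 40 consecutive enrolees each mature, there is no bias. This stands, so a reader who infers that the interim ORR is certainly biased goes further than the text. It does not settle the matter, because 4.7 triggers the interim when a total of 40 have met the status, and 4.5.6.3 says such patients are the ones used. That wording leans towards first to qualify.

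A reader might also infer that the rule makes a false declaration of efficacy more likely. It does the opposite (step 4). Nor does it carry through the trial: enrolment continues regardless, the final analysis waits for every patient to mature, and missing 26/40 stops nothing. SAP 4.5.6.5 plans no hypothesis testing, although 26/40 works as a decision rule.

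The size is open to challenge too. Second-line patients are about 50 to 60 of the 120 in an expanded cohort, so 4 per month implies roughly 8 to 10 per month in a single EBV-positive subtype, while Protocol 3.1 provides for cohorts that enrol nobody in a year. The large losses at 4 and 8 per month should therefore not be quoted as expected.

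Finally, not every non-responder stops early. Stable disease stays on drug and treatment beyond progression is allowed, while some responders leave for transplant or CAR-T, as in the earlier study (Protocol 1.2.4). These patterns shrink the bias; they reverse it only if responders leave sooner than non-responders.

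**Conclusion.** The concern holds in a limited form. The selection rule for the interim set is unspecified, and its natural reading selects patients by a status that failures tend to reach first. On that reading, the interim ORR and its interval are too low whenever non-responders leave treatment sooner.

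Under assumed accrual of 1 to 2 second-line patients per month and a true ORR of 65%, the bias is about 1 to 4 points and P(≥ 26/40) is about 0.39 to 0.54 instead of 0.57. It is larger only with faster accrual, and close to nil if the two groups leave at similar rates. Accrual and time on treatment are assumptions throughout.

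The consequence is lost power for the early declaration and an understated interim ORR. Even if the sponsor intends the first 40 enrolled, the SAP needs to say so. The study is open-label, and the choice of 40 should not remain open once responses are known.

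**What to change.** In SAP 3.3.2, 4.5.6.3 and 4.7, define the interim set as the first 40 second-line patients, by date of first dose, in the primary analysis set (the SAP's modified intent-to-treat set). Set the data cut at the date when the last of these 40 has 6 months of follow-up or has permanently discontinued. Second-line patients dosed later stay out of the interim ORR, whatever their status at the cut.

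The 26/40 threshold, its interval and SAP Table 4 need no change. The cost is wording in three places and a somewhat later interim: about 0.7 to 1.5 months in these runs at a true ORR of 65%, and up to 1.9 months at 45%, so roughly 1 to 2 months under these assumptions.

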4.5.6.4 Multicenter Studies

This is a multicenter study, with approximately 80 sites expected to participate. Efficacy data collected from all study sites will be pooled for data analysis. The effect of study site on the efficacy analysis results may be explored post-hoc, as needed.

4.5.6.5 *Multiple Comparisons/Multiplicity*

There will be no adjustments for multiple comparisons in the efficacy analysis for this study. Results are descriptive in nature, and no statistical hypothesis testing is planned.

There will be no adjustments for multiple comparisons in the efficacy analysis for this study.

4.5.6.6 Use of an "Efficacy Subset" of Patients

The primary efficacy analysis will be performed in the Modified Intent-to-Treat Analysis Set; the Intent-to-Treat and Efficacy Evaluable Analysis Sets will be utilized as sensitivity analyses.

4.5.6.7 Active-Control Studies Intended to Show Equivalence

This study does not include an active-control product and is not intended to demonstrate equivalence between any two drug products.

4.5.6.8 Examination of Subgroups

The primary efficacy endpoint may be summarized by various subgroups of interest based on baseline and demographic categories including age (<65 years of age and \ge 65 years of age), ECOG performance status at study entry (0, 1, and 2), number of prior systemic therapies (1 line and 2+ lines), stage of disease at study entry (Stages 1-2 and Stages 3-4), gender, and race. Summaries by subgroup will only be produced if there are at least 6 patients in the category of interest.

For the post-Stage 2 expansion part of the study, all efficacy analyses will also be summarized in the Modified Intent-to-Treat and Efficacy Evaluable Analysis Sets for the subgroup of patients with second-line EBV⁺ lymphoma as defined in Section 4.1.

Additional subgroup analyses may be performed post-hoc, as appropriate.

4.5.7 Plasma Concentrations

Plasma concentration measurements will be summarized in a separate report and is outside the scope of this SAP.

4.5.8 Pharmacokinetic Analysis

Pharmacokinetic analysis will be summarized in a separate report and is outside the scope of this SAP.

4.6 Safety Evaluation

Safety analysis will be carried out for the Safety Analysis Set as defined in Section 4.2 to include all patients who receive at least one dose of study drug. Patients who do not complete the study, for whatever reason, will have all available data up until the time of study discontinuation included in the safety analysis.

For the Simon 2-stage part of the study, since Cohort 3 (PTCL) patients are initially randomized to monotherapy or combination therapy, their data will be summarized as follows for occurrence-based analyses: patients randomized to monotherapy, patients who start on monotherapy and then cross over to combination therapy, and patients randomized to combination therapy. For analyses presented by study visit, their data will be summarized as randomized.

In addition, all patients who receive combination therapy at any point on study (to include Cohort 3a patients who cross over from monotherapy to combination therapy

during the Simon 2-stage part of the study) will be summarized across both parts of the study separately by cohort and also overall.

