In addition, in prior clinical studies other toxicities reported for one or both agents include fatigue, atrial fibrillation, nausea/vomiting, anemia, leukopenia, and neutropenia.

As QTc prolongation has been reported with other HDAC inhibitors, (Gryder 2012), medications with a known risk of prolonging the QT interval should be avoided (Section 5.5.4).

As with any new combination, toxicities which have not been seen with either agent alone or with combinations of similar agents may become manifest.

Available clinical data indicates a 2- to 2.5-fold higher systemic exposure of nanatinostat with the co-administration of valganciclovir, which is expected, as valganciclovir/ganciclovir is the MDR1 and BCRP inhibitor, and nanatinostat is the substate of MDR1 and BCRP transporters.

The systemic exposure of ganciclovir from nanatinostat and valganciclovir co-administration is consistent with that from valganciclovir monotherapy reported in the literature.

Further information about the safety profile of nanatinostat as a single agent and in combination with valganciclovir can be found in the current IB.

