4.1.2 Summarization by Visit

Data summarized by study visit will be based on the nominal, scheduled visit label as reported on the eCRF. Data collected for the last patient visit will be summarized separately and this summary will be labeled as "End of Treatment" in the analysis.

Data collected at unscheduled visits will not be included in by-visit summaries but will be considered when endpoint derivations potentially include multiple visits (e.g., determination of baseline value, determination of worst post-baseline value, etc.). All data will be included in patient listings.

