4.1.4 Baseline Value

Unless otherwise noted, the baseline value will be defined as the last value reported prior to the first dose of study drug.

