4.5.3 Primary Efficacy Endpoint Analysis Methods

The primary efficacy endpoint is ORR assessed by an IRC.

Patients will be analyzed according to their cohort/lymphoma subtype. For Cohort 3a patients who cross over from monotherapy to receive combination therapy, the CT/PET scan immediately preceding their first dose of combination therapy will be used for their baseline tumor assessment (and not the scan performed at the screening visit).

The number and percentage of patients with a CR or PR after initiation of treatment will be summarized by cohort. Ninety-five percent (95%) confidence intervals (CIs) around the ORR (CR + PR) will be calculated using the Clopper-Pearson method. For patients with measurable disease, a swimmer plot of each patient's overall tumor response assessments during study participation and patient deaths (for those patients who have died) will be presented by cohort.

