4.6.2 Adverse Events

Treatment-emergent adverse events (TEAEs) are defined as those AEs with onset after the first dose of study drug or existing events that worsened after the first dose during the study. Treatment-emergent AEs will be summarized by cohort and over all patients combined.

Specific to Cohort 3a, for patients who cross over to receive combination therapy, events that occur during the monotherapy period will be counted in the Cohort 3a monotherapy subcohort only. Events that occur after the end of monotherapy but prior to the first date of treatment within the combination period will also be counted in the Cohort 3a monotherapy subcohort only. Events occurring after the start of combination therapy will be counted in the Cohort 3a crossover subcohort only.

Events reported with a partial onset date (e.g., month and year are reported but the day is missing) will be considered to be treatment-emergent if it cannot be confirmed that the event onset was prior to the first dose of study drug based on the available date entries.

Verbatim terms on case report forms will be mapped to preferred terms and system organ classes using MedDRA, version 26.0.

Summaries that are displayed by system organ class and preferred terms will be ordered by descending incidence of system organ class and preferred term within each system organ class. Summaries displayed by preferred term only will be ordered by descending incidence of preferred term. Summaries of the following types will be presented:

- Overall summary of number of unique TEAEs and patient incidence of TEAEs meeting various criteria;
- Overall summary of number of unique treatment-emergent serious adverse events (SAEs) and patient incidence of treatment-emergent SAEs meeting various criteria;
- Patient incidence of TEAEs by MedDRA system organ class and preferred term;
- Patient incidence of the most frequently occurring TEAEs (i.e., TEAEs occurring in ≥ 10% of the Safety Analysis Set) by MedDRA preferred term;

- Patient incidence of TEAEs by CTCAE grade, MedDRA system organ class and preferred term;
- Patient incidence of TEAEs by relationship to nanatinostat, MedDRA system organ class and preferred term;
- Patient incidence of TEAEs by relationship to valganciclovir, MedDRA system organ class and preferred term;
- Patient incidence of TEAEs related to nanatinostat by CTCAE grade, MedDRA system organ class and preferred term;

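### By-visit safety values recorded after crossover are reported under Cohort 3a monotherapy, and the 3a response count has no stated cut at crossover

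*SAP*

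**What the plan says.** The first 20 PTCL patients are randomised 1:1 to nanatinostat alone (3a) or with valganciclovir (3b). SAP 3.3.2 states: "Those in Cohort 3a with stable disease at 6 weeks or disease progression at any time will be offered the option to cross over". Protocol Table 6, footnote 1, requires the switch within 7 days of the disease assessment. Patients with CR or PR at Week 6 continue monotherapy.

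Safety data for Cohort 3 follow two different rules:

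- Adverse events (SAP 4.6.2): "Events occurring after the start of combination therapy will be counted in the Cohort 3a crossover subcohort only".
- By-visit tables (SAP 4.6): "For analyses presented by study visit, their data will be summarized as randomized".

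Two general rules bear on the by-visit tables. SAP 4.1.2: "Data summarized by study visit will be based on the nominal, scheduled visit label as reported on the eCRF". SAP 4.1.4, unless otherwise noted: "the baseline value will be defined as the last value reported prior to the first dose of study drug". The safety sections state no new baseline at crossover. SAP 4.6 also provides a further summary, introduced by "In addition, all patients who receive combination therapy at any point on study", which includes the crossover patients.

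For response, SAP 4.5.3 says: "The number and percentage of patients with a CR or PR after initiation of treatment will be summarized by cohort". The same section resets a crossover patient's tumour baseline to the last scan before combination therapy. SAP 4.5 names three Cohort 3 groups (randomised to monotherapy, crossed over, randomised to combination) but does not say where follow-up of the first group ends.

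**The concern.** Cohort 3a exists to show what nanatinostat does alone, and 3a beside 3b is the trial's only randomised contrast. A column labelled monotherapy should hold values measured on monotherapy.

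The parameters at issue can be expected to move when valganciclovir is added. Protocol 1.3.2 lists thrombocytopenia and renal dysfunction as overlapping toxicities and says: "Available clinical data indicates a 2- to 2.5-fold higher systemic exposure of nanatinostat with the co-administration of valganciclovir". In the earlier combination study, 26.6% of patients had raised blood creatinine (Protocol 1.2.4). Followed exactly, the by-visit rule places such values under 3a once patients have crossed over.

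The response count raises a related, smaller question. A 3a patient who crosses over after Week 6 can no longer be seen to respond to monotherapy, whereas a 3b patient with stable disease at Week 8 is rescanned at Weeks 16, 24 and later. Any-time ORRs set side by side therefore rest on unequal opportunity.

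**Working it through.** **1. The plan's own figure.** The plan states no figure for 3a against 3b. The one calculation that covers 3b is the Simon design in SAP 4.7: stop at 1 or fewer of 10, reject at 5 or more of 21.

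P(reject | p) = Σ over x = 2 to 10 of P(X1 = x) × P(X2 ≥ max(0, 5 − x)), with X1 ~ Bin(10, p) and X2 ~ Bin(11, p).

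This gives 0.0440 at p = 10% and 0.8615 at p = 35%, against the stated 0.0440 and 86.2%. It reproduces, and nothing below affects it.

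**2. What each 3a by-visit row contains.** Protocol Table 6 schedules monotherapy visits on Days 1, 15, 29 and 43. A crossover patient then starts combination Cycle 1 Day 1. A Week 6 responder resumes at Day 57, labelled Cycle 3 Day 1 (Table 6, footnote 3). SAP 4.1.2 labels the last patient visit End of Treatment.

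| Row under 3a | Crossover patients | Continuing responders |
|---|---|---|
| Monotherapy Days 15 to 43 | monotherapy | monotherapy |
| Combination Cycles 1 and 2 | combination | none |
| Cycle 3 onward | combination | monotherapy |
| End of Treatment | combination | monotherapy |

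This assumes that the eCRF labels monotherapy visits separately from combination Cycle 1, as the two protocol tables do. The eCRF itself is not among the documents.

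If r of 10 patients respond at Week 6, up to 10 − r can cross over. With r = 2 as an illustration, and all patients still on study, 8 of the 10 values in a Cycle 3 row are combination values.

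**3. Baseline.** For a crossover patient, the reported change splits as follows:

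on-combination value − pre-monotherapy value = (pre-combination − pre-monotherapy) + (on-combination − pre-combination).

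The second bracket arises on the combination but is reported under monotherapy. Displays exposed to this are laboratory summaries and the creatinine and creatinine-clearance plots (SAP 4.6.4), vital signs, QTcF categories by visit and ECOG (SAP 4.6.5).

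**4. Response opportunity.** A 3a patient who crosses over after Week 6 has 1 scan on which a monotherapy response can first be seen. A 3b patient has 3 by Week 24 (Weeks 8, 16, 24) and 5 by Week 48 (adding Weeks 36 and 48).

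Let p be the same true any-time ORR in both arms, and f the share of responses visible by the first scan. If all Week 6 non-responders cross over, 3a is credited with f × p and the gap is p × (1 − f). The documents do not give f. Taking p = 35% and 10 patients per arm (two independent binomials):

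| f | 3a ORR | Gap (points) | P(3b has more responders) | P(3a has more) |
|---|---|---|---|---|
| 1.0 | 35% | 0 | 41% | 41% |
| 0.8 | 28% | 7 | 54% | 28% |
| 0.6 | 21% | 14 | 68% | 17% |
| 0.5 | 17.5% | 17.5 | 74% | 12% |

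Over the same range of f, the gap is 0 to 5 points at p = 10%, 0 to 13 at p = 26% and 0 to 23.5 at p = 47%. In the other direction, each post-crossover response credited to 3a would add 1/10 = 10 points. For scale, the Clopper-Pearson 95% interval for 3/10 is 7% to 65%.

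**The case against.** The strongest reply is that no 3a–3b comparison is planned. SAP 4.1.1 excludes formal comparison of cohorts, SAP 4.5.6.1 and 4.5.6.5 call the results descriptive, and Protocol 9.1 only has the two sub-cohorts summarised separately. That stands: no error rate or enrolment decision depends on these tables. A descriptive column must still describe the treatment on its label.

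A reader might infer that monotherapy safety as a whole is contaminated and the difference from the combination is hidden. The documents do not support that:

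- The Day 15 to 43 rows hold monotherapy data only.
- Adverse events are split at crossover, and under Protocol 8.1.1 laboratory abnormalities that need treatment, interruption or dose modification are adverse events.
- The worst-post-baseline shift tables are not clearly governed by the by-visit sentence; they simply lack a stated rule.

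The all-combination summary is also offered as an answer. It shows crossover values in a second place but does not take them out of 3a.

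On response, a reader might infer that post-crossover responses will be credited to monotherapy. The SAP points the other way: 4.5 makes crossovers a separate group, 4.5.3 resets their tumour baseline, and 4.5.4 applies DOR and DOCR to them only after crossover. What is missing is one explicit sentence. Nor can a reader conclude that any 3b advantage would be an artefact. The unequal opportunity follows from the crossover design, crossover is optional, and its effect may be nil. Protocol 1.2.4 says most responses in the earlier combination study were seen by the first assessment. Protocol 1.2.3.1 also gives reason to doubt a 35% response rate on nanatinostat alone.

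**Conclusion.** The safety point holds as an inconsistency within the SAP. By-visit values taken on the combination are reported as Cohort 3a monotherapy against a pre-monotherapy baseline, although adverse events and the tumour baseline are handled by period. It affects the post-crossover rows of descriptive tables, with mixing mainly from Cycle 3 onward and at End of Treatment. How many values are involved depends on how many patients cross over and on the eCRF labels, neither of which the documents give.

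The response point is secondary. The cut for 3a should be stated. The possible gap of 0 to 17.5 points rests on an assumed equal ORR of 35%, crossover by every Week 6 non-responder and an assumed early-response share of 100% to 50%. It may be small, and 10 patients per arm could neither show it nor rule it out. The point is worth correcting but threatens no primary conclusion.

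**What to change.** In SAP 4.6, apply the 4.6.2 cut to all Cohort 3 by-visit summaries, including the creatinine and QTcF displays. Close the 3a monotherapy column at the first combination dose. Show later values in the crossover group, with change from the last pre-combination value. State the same cut for the worst-post-baseline shift tables.

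In SAP 4.5.3, state that only IRC responses before crossover count for patients randomised to monotherapy. Beside the any-time ORR, add a descriptive row with IRC response at the first scheduled scan (3a Week 6, 3b Week 8) in the same analysis set. Note under the table that 3b still has two weeks more.

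The cost is SAP wording, a period flag that the adverse-event tables already need, and a few table rows from data already collected. The any-time ORR for 3b and the Simon decision rules do not change. The first-scan figure for 3b may look less favourable than its any-time ORR.
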